Demonstrating results are possible with 4 mA, which may be superior or unachievable with 2 mA, would persuade other researchers to also explore if the improvement (or the lack thereof) in their own tDCS studies would be present or larger using 4 mA tDCS. Over time, just as tDCS researchers began favouring 2 mA over lower intensity levels, 4 mA rather than 2 mA could become the new convention. Also, by exploring how individual differences impact the response observed, we can target those individuals who are expected to most benefit from tDCS. In this manner, tDCS studies can become more efficient.

[figure not shown]
Hypotheses Addressed

- The degree of improvement observed in people with Alzheimer's disease will be significantly greater when training is carried out at higher stimulation intensity (4mA vs. 2mA, SHAM).
- There will be significantly more significant improvement observed when:
 1. individuals have more atrophy (decreased brain volume, higher CSF volume).
 2. Individuals have a higher degree of impairment.
 3. The participant is female.

PRELIMINARY STUDIES

The proposed study models after our original three-round study [5] where three different tDCS montages were compared for improving naming ability. We recently completed another three-round study [31] where a mixed group of people with dementia (AD and FTD) concluded three consecutive rounds of executive function training with either: 4mA tDCS targeted towards the left dorsolateral prefrontal cortex (DLPFC), 2mA tDCS via two anode electrodes to the left and right DLPC respectively, or SHAM stimulation, which is the accepted placebo condition in tDCS studies. In SHAM stimulation, tDCS is only briefly active at the beginning and end of the session, which mimics the real-life sensation of tDCS as feelings are felt mainly only at the beginning and end of the session when the current is ramping up or down. We measured how much participants improved on an N-Back task, defined as having faster response times. For evaluation, participants completed two versions of this N-Back task: one practiced during the tDCS sessions, and another never practiced and was only given during evaluations. For trained items, results were similar regardless of stimulation condition, but the most significant improvement was found for the 4mA condition for untrained items.

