Because the bilateral montage delivered 2mA to each anode electrode over the left and right DLPC, finding superior results for the unilateral 4mA condition could be related to the involvement of the right DLPFC being stimulated, or due to a stronger intensity level being administered. The study proposed here will investigate the latter hypothesis: results were due to a more vigorous tDCS intensity (i.e., 4mA).

METHODS:

Sample

Based on pilot data, we expect a pooled standard deviation for response time on the N-Back test of 3,000 ms and a correlation of 0.89 between adjacent time points (pre, post, follow up). For 80% power to detect a difference across the three levels of intensity, while also accounting for the sex of a participant, a repeated-measures ANOVA test at an alpha level of 5% will require 54 participants with AD (27 men and 27 women). To compensate for anticipated attrition over the study, we will recruit a sample of 30 men and 30 women, 60 total, randomized into the three treatment arms. These participants would have received the diagnosis of probable AD from Baycrest's Memory Clinic expert staff [32, 33] according to standard clinical criteria. Only patients with no family history of epilepsy and who can give consent will be tested. We will seek people with mild to moderate AD (Reisberg stages 3, 4, or 5, [34]). Participants must show no history of stroke or traumatic brain injury, nor shunts or metal in the head that could interfere with the delivery of tDCS. Finally, people will have no evidence of significant heart disease, alcoholism, drug use. All

enrolled participants will be expected to complete an MRI; however, if they are unable to complete an MRI due to the presence of an exclusion criterion, they will still be allowed to complete all subsequent stages of the study. In the initial assessment, we will verify participants can complete the study task (N-Back). Only individuals able to complete this task will be allowed to complete the study.

Recruitment and Pre-Assessment

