Participants will be asked to arrive 15 minutes before their scheduled scan to review and fill the consent and MR screening forms. The participant will then be escorted to the Interview room to be interviewed by a Level 11 MR Personnel with respect to their MR screening form and medical history prior to changing for the MR exam. After changing, the MR technologist will escort the research participant into the magnet room and the accompanying researcher (Assistant, Coordinator or PI) to the control area. Post scanning, the lab member accompanying the research participant will monitor the change process, and other processes outlined in the “MR Research Suite Process Bacycrest – RRI.”

To be able to successfully perform the MRI, lab members will undergo the Virtual MR Safety Training & Orientation session and will also receive an in person suite tour.

Planned Analyses

The primary outcome measure will be improvement on an N-Back Task, both a trained version and an untrained version. Improvement will be measured in terms of the average response time (i.e., the amount of time needed to make a response). A repeated-measures ANOVA will be run to compare the three stimulation conditions (SHAM, 2mA, 4mA) with sex (male, female) as a between-subject variable. This analysis will be conducted separately for the trained and untrained items. Scheffé tests will compare the different conditions. We expect to find the greatest improvement in the 4mA condition.

Next, we will calculate a tDCS time improvement score for each participant per condition: the difference between the final average response time on the N-Back task from the last stimulation session subtracted from the baseline response time in each condition. To produce tDCS *effectiveness scores*, the time improvement score in the SHAM round will be deducted from the number calculated in each real tDCS round. In other words:

- Time Improvement in the 4mA condition *minus* Time improvement in the SHAM condition;
- Time Improvement in the 2mA condition *minus* Time improvement in the SHAM condition.

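### Do two primary N-Back versions, sized as one 5%/80% ANOVA, need a stated rule for a split result?

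*Protocol*

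**What the plan says.** Under Planned Analyses the protocol defines the primary outcome over two versions of the task: "The primary outcome measure will be improvement on an N-Back Task, both a trained version and an untrained version". Improvement is measured by average response time. The ANOVA compares SHAM, 2mA and 4mA with sex as a between-subject factor, and "This analysis will be conducted separately for the trained and untrained items". Within each ANOVA, "Scheffé tests will compare the different conditions". No order, alpha split or joint success rule is given.

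The intensity hypothesis under Hypotheses Addressed is a single statement, that improvement "will be significantly greater when training is carried out at higher stimulation intensity", and it names neither version.

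The Sample section gives one calculation. It takes "a pooled standard deviation for response time on the N-Back test of 3,000 ms" and a correlation of 0.89 between adjacent time points. "For 80% power to detect a difference across the three levels of intensity", it arrives at 54 participants (27 men, 27 women) and recruits 60. It states no effect size and no version.

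Baseline Evaluation says what each version is for: the trained one shows the effect of tDCS on training, the untrained one shows whether that effect generalises.

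**The concern.** A sample size built on one test does not automatically serve a primary outcome made of two. If the intensity hypothesis needs both versions, the stated 80% is too high. If one is enough, two tests at 5% carry more than 5% error. Only with one version named as primary would both figures hold for a single trial-level verdict, and the protocol names none.

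A split result is also plausible. Preliminary Studies reports one from the team's earlier study: "For trained items, results were similar regardless of stimulation condition", while the largest improvement on untrained items was at 4mA. If that recurs, the protocol does not say whether the intensity hypothesis is supported, and the emphasis could be chosen after the data are seen. The section on communication of results speaks of showing the effectiveness of 4mA in general, which suggests a single statement.

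**Working it through.** **Inputs.** From the Sample section: N = 54 in two sex groups, alpha 5%, power 80%. From Planned Analyses: three conditions, two separate ANOVAs, Scheffé comparisons. Assumed: normal errors, sphericity, 5% for each ANOVA and for Scheffé, and a between-version correlation r from 0 to 0.9, since the protocol gives none.

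**The plan's own figure.** The 54 cannot be reproduced without an effect size, so the effect is solved backwards. The within-person F test has 2 and 2 × (54 − 2) = 104 degrees of freedom and a 5% critical value of 3.084. Power of 80% needs a noncentrality of 9.92, which is held fixed below. The recruitment figure implies 10% attrition: 54 / 0.90 = 60.

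**If a joint rule is imposed.**

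| Rule | r = 0 | r = 0.9 |
|---|---|---|
| Both versions significant, planned effect on both | 0.80² = 64% | about 75% |
| Either significant, no true effect | 1 − 0.95² = 9.75% | about 7% |

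These figures are right for those rules. They concern the overall F test, which says only that the three conditions differ somewhere.

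**False claims under the plan as written.** The hypothesis is directional, and the comparisons of 4mA with 2mA and with SHAM are made by Scheffé. The Scheffé critical value for a pair is √(2 × 3.084) = 2.483 on 104 degrees of freedom, which leaves 0.73% in one tail.

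- One version, two comparisons favouring 4mA: at most 2 × 0.73% = 1.46%.
- Both versions, four comparisons: at most 4 × 0.73% = 2.92%, whatever r is.
- Simulation with no true effect, either version: about 2% to 3%.
- If 4mA must beat both 2mA and SHAM on the same version: about 0.1% to 0.2%.
- Any false pairwise difference, in any direction and on either version: about 5.6% to 7.7%. This exceeds 5%, but most of it is not a claim for 4mA.

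**Split results.** With the planned effect on untrained items and none on trained, the F tests split in 0.80 × 0.95 + 0.20 × 0.05 = 77% of trials at r = 0, and about as often at higher r. With half the effect on trained items the figure is about 54% to 64%. These too are overall-F results rather than verdicts on the hypothesis. At the same noncentrality, Scheffé power on one version for 4mA to beat both other conditions is about 18% if the means are equally spaced and about 44% if only 4mA differs.

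**What a stated rule would cost.**

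- Fixed order, second version tested only if the first is significant: a benefit confined to the second version passes both steps in about 0.05 × 0.80 = 4% of trials at r = 0. If trained items came first, that would be the pattern of the earlier study.
- Holm across the two F tests: an effect on one version has power of about 71% instead of 80%. Regaining 80% needs about 65 evaluable participants (66 with equal sexes), or 66 / 0.90 = 73.3, so 74 recruited. If the verdict rests on the F test, the rule also ignores direction, so a result with 4mA worst would count as support.

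**The case for a change.** The best case for a change is that a SAP can add a multiplicity rule but cannot repair the sample-size statement. The primary outcome and the 54 both stand in the protocol, and under either joint rule the 5%/80% pair would be wrong for the trial as a whole. The earlier study's split makes the question real, and one sentence would settle it without extra participants.

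Part of this stands. The protocol gives no hierarchy, does not say which version the SD and correlation came from, and does not say how a split bears on the single hypothesis. A line on each would help a reader.

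It does not amount to a contradiction. The mismatch arises only after a both-must-succeed or either-suffices rule is added, and no section contains one. Separate ANOVAs with separate purposes fit a calculation that describes each ANOVA. A split can also be reported as it stands: an effect on training without generalisation, or the reverse. On the unnamed version, Training Sessions says that the versions differ only in their stimuli and gave similar response times and errors in normal elderly controls. That is partial support for one SD, since the controls were not patients. The sentence on communicating results concerns publication and is not a decision rule.

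**Conclusion.** No change to the plan follows. The Sample section's figures are consistent with each version's ANOVA taken separately, provided that the 3,000 ms SD and the 0.89 correlation apply to both versions. Followed as written, the plan keeps a false claim for 4mA over either comparator, on either version, at or below 2.92%, given normal errors, sphericity and Scheffé at 5%. The 64% to 75% joint power and the 7% to 9.75% error belong to rules the protocol does not adopt.

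What remains is an unwritten hierarchy or multiplicity rule. A protocol commonly leaves that to the SAP, which was not available here, and analysts can fill the gap sensibly by reporting a conclusion on 4mA for each version from the directional comparisons. Imposing an order or Holm would be a debatable trade-off: about a 4% chance of claiming a benefit confined to the second-ranked version, or 71% power instead of 80%, to control an error that is already small. The missing effect size, which prevents a check of the 54, is a separate matter.

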Stimulation will be delivered for 20 minutes concurrent with the beginning of the session, with the anode electrode placed over the left DLPC and the cathode over the right DLPC.

Figure 1 (below). Dorsolateral Prefrontal Cortex Montage. Activation prediction based on modeling software from Soterix HD-Explore; color gradients reflect increasing levels of predicted intensity, where red reflects a peak intensity of 0.61 mA.

Study Design

Participants will be randomized into three treatment arms. Participants will complete three rounds of executive function training in each arm, with each round paired with different stimulation intensity (SHAM, 2mA, 4mA). The below flowchart displays the procedure that participants will follow:

Initial Assessment

In the first week, all participants will receive an initial assessment to gather demographic information (age, sex, years of education, racial background, and hand preference) and conduct a formal evaluation of participants. Evaluation includes the Montreal Cognitive Assessment (MoCA; [26]) and the Mini-Mental State Exam (MMSE; [27]) to assess the level of cognitive function, as well as a practice version of the study task (N-Back) where they must state via a button press on a computer if the presented image is the same or different from the previous image. This is to ensure the participants can complete it in the upcoming study rounds. From these tasks, participants' impairment scores will be calculated. *Cognitive severity* will be measured as the combined total from the MoCA and MMSE ($x/30 + x/30$). In contrast, *baseline severity* will be measured as the

average response time on the practice version of the N-Back. Assuming inclusion criteria are met, participants in the first week will also complete a structural MRI [view MRI protocol – page 11]. We will use SPM 12 to quantify head and tissue layers, including CSF, which will be quantified relative to the participant's skull size. For skull thickness and grey matter, we will quantify regions around the left DLPFC.

Baseline Evaluation

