give sham or tDCS set at 2mA or 4mA for 20 minutes and will remain during the session with the participant for safety precautions and troubleshoot any computer problems. Simultaneously with the stimulation, participants will use the computer to practice the given N-back task. This N-back task is modeled off of the 1-back version of the N-back Matching Task [41]. In that study, participants were asked whether a presented digit (e.g., a red 5) was the same as the previously shown digit (either a red five or some other number-color combination); they gave their response by pressing a key on a keyboard to indicate if the number is the same (i.e., a red 5), or different (i.e., something other than a red 5). Following Basak and O'Connell [42], we have created different versions of this task but use images (animals, fruits, vehicles, faces) rather than numbers to make the task slightly easier for people living with dementia. The only difference between these versions is the stimuli presented. We also have normed these versions with normal elderly controls and found that response times and errors were similar for all versions. In each round, participants will practice a different version of the N-Back. Evaluations specific to that round will also administer a round-specific untrained list.

Subsequent Evaluations

For each round, in addition to the evaluation just before the first stimulation session, an additional evaluation will take place during the final training session, and two weeks later after the final session. In this manner, we can obtain a baseline measurement, check for post-stimulation changes, and if those changes have continued two-week's post-stimulation.

Structural MRI Protocol

Participants will undergo a Structural MRI at Baycrest. The protocol has been informed to the MR Technicians (please see attached documents). The Project Coordinator will book the MR suite using the Baycrest MR Web Scheduler with a 72 hour notice at the least.

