Thus, a tDCS effectiveness score is calculated for each participant in the 4mA and 2mA conditions. These tDCS effectiveness scores will then be the dependent variables in a multivariate logistic regression; once for trained items, again for untrained items. The predictors will be the CSF level of a participant, grey matter volumes and skull thickness around the DLPFC, impairment scores (baseline and cognitive severity), and interactive terms representing the sex of the participant. In this manner, we can examine what individual differences predict the tDCS response in people with AD and if these predictors are the same for two and 4mA tDCS while checking for sex differences. We expect more significant levels of CSF, less DLPFC grey matter, thicker skulls, and greater impairment levels will be predictive of more substantial improvement in the 4mA condition. CSF and grey matter values may be less predictive for how well women respond to tDCS as their relatively smaller heads could compensate for increased shunting levels. Finally, a 2 (male AD, female AD) x3 (4mA, 2mA, SHAM) between-subject repeated measures ANOVA will be run for tasks administered in evaluation: MoCA scores, to check for changes in general cognition, as well as for verbal fluency, digit span, and Corsi to check for generalized executive function differences. These analyses are exploratory.

Funding

This study is supported by BrightFocus Foundation, which reviewed the submitted protocol, and awarded funds to [name] [name] towards completing the proposed study.

Risks

The tDCS protocol for this experiment was determined according to the best practices observed in previous research using tDCS stimulation [45]. Furthermore, tDCS is safe, has virtually no side effects,

is technically easy to carry out, and is not uncomfortable to undergo [46,47]. Multiple studies have also reported that the administration of 4 ma tDCS has no more adverse effects than 2 ma tDCS [48]. No incidence of seizure has been recorded, although side effects could include headache, drowsiness, itching sensation, nausea, and, in rare cases, disorientation. In our experiences, the only observed and reported side-effect has been temporary redness post-stimulation where the sponge was placed, as well as the occasionally reported headache.

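### The primary ANOVA of a three-round crossover has no term for round, so any difference in N-Back gain between rounds inflates the error and can cost power

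*Protocol*

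**What the plan says.** Protocol, Study Design, describes a within-participant crossover: "Participants will complete three rounds of executive function training in each arm, with each round paired with different stimulation intensity (SHAM, 2mA, 4mA". Subsequent Evaluations gives each round its own baseline ("For each round, in addition to the evaluation just before the first stimulation session"), a second evaluation at the final training session and a third two weeks later. Training Sessions adds that the N-Back version changes with each round. It reports that the versions were normed in healthy older controls with similar response times and errors.

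Planned Analyses makes N-Back improvement, measured by average response time, the primary outcome and names the model: "A repeated-measures ANOVA will be run to compare the three stimulation conditions (SHAM, 2mA, 4mA) with sex (male, female) as a between-subject variable". This is run separately for trained and untrained items. The exploratory outcomes get a 2 (sex) by 3 (condition) "between-subject repeated measures ANOVA will be run for tasks administered in evaluation". Neither model has a term for round, period, order or arm.

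Sample gives the planning inputs: "pooled standard deviation for response time on the N-Back test of 3,000 ms and a correlation of 0.89 between adjacent time points", and the target: "For 80% power to detect a difference across the three levels of intensity, while also accounting for the sex of a participant". It concludes that 54 participants are needed and recruits 60 to allow for attrition.

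**The concern.** In a crossover, each within-participant comparison of conditions is also a comparison of rounds. Three rounds of practice on the same kind of task, with different stimuli each time, could well produce different gains: less room to improve later, a learned strategy carried forward, or fatigue. The norming exercise does not settle this. It concerned response times and errors in healthy controls, not training gain in people with Alzheimer's disease over repeated rounds.

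The fresh baseline deals with a change in level. It does not deal with a change in gain. If gain differs by round and the model has no round term, that systematic variation is treated as noise when conditions are compared. Intervals become too wide, the type I error falls below 5%, and power falls below the planned 80%. If completers are unequal across the orders, part of the round effect also enters the condition contrasts as bias.

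**Working it through.** **Inputs from the protocol (Sample).** SD of response time 3,000 ms; correlation 0.89 between adjacent time points; alpha 5%; power 80%; N = 54, recruited 60.

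**The plan's own figure.** The 54 cannot be reproduced, because no detectable difference is stated. The effect is therefore back-solved to give 80% power at N = 54 when there is no round effect.

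**Assumptions, not in the documents.** Three position-balanced orders of 18 completers; gain changing linearly by a step *s* per round; the 2mA effect midway between SHAM and 4mA; gains correlated 0 or 0.5 between rounds. The outcome analysed is the within-round gain. A condition-by-time interaction over pre and post gives the same test.

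**Step 1, SD of the gain.** 3,000 × √(2 × (1 − 0.89)) = 1,407 ms, variance 1,980,000 ms². With gains uncorrelated between rounds, the residual SD is 1,407 ms. With correlation 0.5 it is 1,407 × √0.5 = 995 ms, variance 990,000 ms².

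**Step 2, implied effect.** The error df are (54 − 2) × 2 = 104. For a 4mA − SHAM difference *d*, the noncentrality is 54 × (*d*²/2) / residual variance. Power of 80% needs *d* = 853 ms (SD 1,407) or 603 ms (SD 995).

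**Step 3, error inflation when round is omitted.** With balanced orders, round is orthogonal to condition, so all round variation goes into the error:

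E(MSE) = σ² + 54 × 2*s*² / 104.

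At *s* = 500 the added term is 54 × 500,000 / 104 = 259,615 ms², which is 13% of 1,980,000 and 26% of 990,000. At *s* = 1,000 it is 1,038,462 ms², or 52% and 105%.

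**Step 4, power of the condition F test by simulation (60,000 runs, N = 54).**

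| Change in gain per round (ms) | Without round, SD 1,407 | With round, SD 1,407 | Without round, SD 995 | With round, SD 995 |
|---|---|---|---|---|
| 0 | 80.0% | 80.0% | 80.0% | 80.0% |
| 100 | 79.7% | 79.9% | 79.5% | 79.8% |
| 250 | 78.8% | 80.0% | 77.6% | 80.0% |
| 500 | 75.0% | 79.9% | 70.0% | 79.9% |
| 750 | 68.9% | 79.9% | 57.4% | 79.9% |
| 1,000 | 59.8% | 80.1% | 40.5% | 79.9% |

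**Step 5, type I error (20,000 runs, SD 1,407).** Without round it is 5.0, 4.5, 3.1, 2.1 and 1.0% at 100, 250, 500, 750 and 1,000 ms per round. With round it is 4.8 to 5.0%.

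**Step 6, completers needed for 80% power without round (steps of 3, 40,000 runs).** At 250, 500, 750 and 1,000 ms per round: 57, 60, 69 and 78 (SD 1,407); 57, 66, 81 and 99 (SD 995).

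**Step 7, bias when completers per order are unequal.** In a three-order Latin square, the position of 4mA minus that of 2mA is +1, +1 and −2 (or the reverse) across the orders. With 20/18/16 completers and the smallest group in the −2 order, the mean imbalance is (20 + 18 − 2 × 16)/54 = 6/54. At 1,000 ms per round that shifts 4mA − 2mA by 111 ms, or 13% of 853 ms. With 19/18/17 it is (19 + 18 − 2 × 17)/54 = 3/54, or 56 ms. The sign depends on which order loses people, and some patterns cancel. With round in the model the bias is about zero.

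**The case against.** The strongest reply is that harm is not shown from the documents. Nothing in them says that gain differs by round. At 250 ms per round or less the loss is at most about 2 points of power, and the error is on the conservative side, so no false positive follows. The scenarios that hurt are large: 500 ms per round means a 1,000 ms difference between rounds 1 and 3, more than the whole back-solved 4mA − SHAM effect of 853 or 603 ms. That effect is itself an assumption, and a larger planned difference would shrink the loss. If the pilot SD and correlation were pooled over rounds, they may already contain some round variation. The bias is proportional to the step: at 250 ms per round the two figures become about 28 and 14 ms, against a standard error of 1,407 × √(2/54) = 271 ms. The order of intensities in each arm is not given in the text, so balance is assumed. Finally, a statistical analysis plan could add the term.

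These points limit the size, and they stand to that extent. They do not remove the point. The protocol does not merely leave the model open: it names its factors, and round is not among them. No scenario examined shows a meaningful advantage to leaving round out, because with no round effect power is 80.0% either way. A later plan may add the term, but that would be a change to the model stated here.

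**Conclusion.** The point holds as a possible loss of power, not a demonstrated one. The stated model omits a factor that the design creates. The cost is negligible if gains change by 250 ms per round or less. It is material from about 500 ms: 75% or 70% power instead of 80%, depending on whether gains correlate 0 or 0.5 between rounds. At 500 ms and residual SD 1,407 ms, the stated model needs about 60 completers, which is the whole allowance for attrition. With balanced orders the condition estimates stay unbiased and the test is conservative. With modestly unequal completion there is also a bias, small unless the round effect is large.

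The figures rest on balanced orders, a linear change in gain, the two assumed correlations and an effect back-solved to 80% power. The direction of the power loss under balanced orders does not depend on the particular values. This should be fixed because the protection costs almost nothing. The same gap in the exploratory ANOVAs matters less, since they carry no power target.

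**What to change.** In Planned Analyses, add round (1, 2, 3) as a fixed within-participant effect to the primary analysis of trained and of untrained items. One form is a linear mixed model of within-round improvement with condition, round, sex and condition-by-sex as fixed effects and a random participant effect. Randomised order can be an optional between-participant term. Use the same structure for the exploratory repeated-measures analyses.

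The cost is a change of wording and 2 error degrees of freedom (104 to 102). No new data are needed, and if there is no round effect power is unchanged at 80.0%.

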If the event were to result in lasting pain and hospitalization, then it would be reported as a ‘Serious Adverse Event’ and full details would be noted to the research ethics board as well as Health Canada. These events would be recorded on the worksheets being used to collect the rest of the data. We must stress, however, that after administering 4 mA tDCS to around 60 participants, for hundreds of tDCS sessions, we have never encountered any such event. Although we have safety protocols in place for any encountered adverse or severe adverse events, we believe such events will fail to occur in the present study.

Confidentiality

A research study file as well as medical records identifying participants will be maintained within [name] lab. Names and identifying information will be replaced with a code, and the information will be kept on file for 10 years after the end of the study. Data collected from participants’ who withdraw from the study will also be kept, unless participants withdraw consent for its use.

Communication and Publication of Research Results

The found results may be presented at research conferences and written up in a manuscript submitted for a publication in a respected science journal. The data will never be used for commercial goals and all participant information will remain confidential. Individual’s participant data will be presented using a code (e.g., Participant 1), which ensures no reader of the data could identify the participant. The results found can also be used to back-up further studies involving 4 mA tDCS because

we will be able to present formal data demonstrating its effectiveness compared to other intensities of stimulation (SHAM, 2mA) in people with Alzheimer's Disease.

REFERENCES:

2. Zortea, M. et al. Transcranial Direct Stimulation to improve the dysfunction of descending pain modulatory system related to opioids in chronic non-cancer pain: An integrative review of neurobiology and meta-analysis. *Frontiers in Neuroscience*. 2019. 13(128)
3. [name], C., et al. tDCS stimulation alongside picture training improves naming scores in anomic dementia patients. in *Alzheimer's Association International Conference*. 2015. Washington.

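### The repeated-measures ANOVA and the SHAM-deducted scores leave out completed rounds of people who withdraw early; a mixed model with period on all completed rounds would use them at almost no cost.

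*Protocol*

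**What the plan says.** Under Study Design, every participant goes through all three intensities: "Participants will complete three rounds of executive function training in each arm, with each round paired with different stimulation intensity (SHAM, 2mA, 4mA". Under Planned Analyses, the main comparison is set out as follows: "A repeated-measures ANOVA will be run to compare the three stimulation conditions (SHAM, 2mA, 4mA) with sex (male, female) as a between-subject variable". It is run separately for trained and untrained items, with Scheffé tests between conditions. The same section then builds effectiveness scores for 4mA and 2mA: "the time improvement score in the SHAM round will be deducted from the number calculated in each real tDCS round". These scores "will then be the dependent variables in a multivariate logistic regression".

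The Sample section names the same ANOVA as the basis of the sample size ("a repeated-measures ANOVA test at an alpha level of 5% will require 54 participants with AD (27 men and 27 women") and expects losses: "To compensate for anticipated attrition over the study, we will recruit a sample of 30 men and 30 women, 60 total". Under Confidentiality, the data of people "who withdraw from the study will also be kept, unless participants withdraw consent for its use".

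**The concern.** A classical repeated-measures ANOVA with three within-person levels needs a value in each level, so a person who lacks one round contributes nothing. The effectiveness scores have a similar limit. Without the SHAM round neither score exists. Without one active round only the other score exists, and a joint fit of both scores then drops the person as well.

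Which rounds survive a withdrawal therefore depends on the randomised order. Someone with SHAM last who leaves after two rounds has no score. Someone with SHAM first who leaves after two rounds keeps one. A 4mA result followed by withdrawal is dropped from the ANOVA if 4mA came first or second, and is kept if 4mA came last. At stake are precision in every case and, under a particular pattern of leaving, the direction of the 4mA comparison.

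**Working it through.** **Inputs from the protocol (Sample section).** 54 required and 60 recruited; alpha 5%; SD of response time 3,000 ms; correlation 0.89 between adjacent time points.

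**Inputs assumed, because the protocol does not give them.** Three Latin-square orders of the conditions; correlation between a person's improvement scores in different rounds of 0.1 to 0.5; no true difference between conditions; leaving only after a completed first or second round.

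**The plan's own figures.** 54 / (1 - 0.10) = 60, so recruitment matches 10% attrition. The 54 itself cannot be reproduced, because no effect size is stated.

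**Rounds lost.** Six leavers with one or two completed rounds each lose 6 to 12 rounds. The 54 completers supply 54 × 3 = 162. The unused share of the data in hand is 6/168 = 3.6% to 12/174 = 6.9%.

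**Scale.** SD of improvement = 3,000 × √(2 × (1 - 0.89)) = 1,407 ms. The standard error of 4mA minus SHAM in 54 completers is 1,407 × √(2 × (1 - r)) / √54:
- r = 0.1: 1,407 × 1.342 / 7.348 = 257 ms
- r = 0.5: 1,407 × 1.000 / 7.348 = 191 ms

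**Leaving unrelated to outcome.** There is no bias. Compared with a mixed model on all completed rounds, the complete-case variance of 4mA minus SHAM is about 3-6% larger at 10% attrition and about 7-10% larger at 20%.

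**Leaving linked to outcome (simulated trials of 60).**

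| Trigger for leaving | Attrition | Complete-case bias, 4mA minus SHAM |
|---|---|---|
| Poor 4mA round only, odds ×2 to ×4 per SD of poorer gain | 10% | about +40 to +135 ms |
| Same | 20% | about +84 to +246 ms |
| Poor round of any condition, odds ×4, r = 0.3 | 10% | +5 ms (simulation noise) |
| Same | 20% | +1 ms (simulation noise) |

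The 4mA-only bias at 10% runs from about 40/191 = 0.2 to 135/257 = 0.5 of a standard error. It shrinks as r rises. A more extreme rule, in which only the worst 4mA responders leave, gives +95 to +242 ms at 10% (r from 0 to 0.6).

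**False positives under the planned tests.** For three conditions the Scheffé limit is √(2 × F), with F(0.95; 2, 104) = 3.08, so √6.16 = 2.48. With no bias, one pairwise contrast exceeds this in a given direction about 0.7% of the time. Under the 4mA-only trigger the rate favouring 4mA is about 1-3% at 10% attrition and about 2.6-5.8% at 20%.

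**Which mixed model.** Early leaving unbalances condition against round, and gains may shrink as training is repeated. Take a fall in gain of 300 to 700 ms per round (assumed) and the 4mA-only trigger. A mixed model without period is then biased by about -30 to -137 ms. Adding period brings the bias to within about 6 ms.

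**The case against.** The strongest reply is that handling of incomplete rounds belongs in a SAP, that the protocol nowhere says dropouts are excluded, and that recruiting 60 already covers the expected loss. This stands in part. The absence of a missing-data rule is no finding, and a SAP could soften the effect. But the protocol itself names the method, and the classical form of that method cannot use a person with a missing round. Over-recruitment restores the number of completers, but it does not use the rounds already collected from the others.

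A reader might go further and infer that the plan is biased in favour of 4mA. The documents do not support that. It would need leaving to follow poor 4mA rounds and not poor SHAM or 2mA rounds. Baseline Evaluation says participants are not told their intensity. Risks cites evidence that 4mA has no more adverse effects than 2mA. When a poor round of any condition can prompt leaving, the bias disappears.

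A reader might also infer a marked rise in false positives. Unadjusted paired tests would show about 4-7% against a nominal 2.5% at 10% attrition, but the protocol plans Scheffé tests, for which the figure is about 1-3%.

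Nor does the Confidentiality statement contradict the analysis. It concerns keeping records and promises nothing about their use in a model. It shows only that the data would be available.

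**Conclusion.** The point holds as an inefficient choice of method. At the implied 10% attrition the certain cost is about 3-6% more variance, with the standard error about 1.5-3% larger (√1.03 = 1.015, √1.06 = 1.030). Bias is conditional: about 40-135 ms in favour of 4mA if poor 4mA rounds alone prompt leaving, and none of note if any poor round does. Leaving tied to poor SHAM or 2mA rounds would push the other way.

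These sizes rest on the assumed orders, the assumed correlation between rounds, and leaving only between rounds. The 20% figures are a stress case with no source in the protocol. The case for change is that a better method is available for a few lines of text.

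**What to change.** In Planned Analyses, make the primary analysis a linear mixed model fitted by REML to every completed round of every randomised participant, separately for trained and untrained items as now planned. Use condition, sex, condition-by-sex, period (round) and sequence as fixed effects, with a participant random effect or an unstructured within-person covariance. Take 4mA minus SHAM, 2mA minus SHAM and 4mA minus 2mA as contrasts of that model, and keep the planned multiplicity control. Report the complete-case ANOVA as a sensitivity analysis, and list withdrawals by the condition of the last round attended.

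The cost is wording only: no new visits or data, since withdrawn participants' data are already retained unless consent is withdrawn. The downside is small. The model relies on data missing at random, and it does not correct for people who leave during a round before its final evaluation. The listing of withdrawals helps the reader judge that case.
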